Bogosinubia	105,780	741,457	782,060	Non-PBO
Gemena	232,158	741,457	549,902	PB0
Libenge	146,629	594,828	549,902	Non-PBO
Mawuya	97,755	497,073	549,902	Non-PBO
Mbaya	40807	497,073	509,095	PBO
Tandala	177,066	497,073	332,029	PBO
Bulu	90,793	406,280	332,029	Non-PBO
Kungu	137,104	269,176	332,029	Non-PBO
Bangabola	119,323	269176	212,706	PBO
Bominenge	97,143	172,033	212,706	Non-PBO
Bokonzi	136,110	172,033	76,596	PBO
Ndage	85,008	87,025	76,596	Non-PBO
Boto	113,992	-26,967	76,596	87,025 Non-PBO + 26,967 PBO

Randomisation and proposed LLIN-type distribution plan

Zongo	49607	-26,967	26,989	PB0	
-------	-------	---------	--------	-----	--

The proposed assignment uses the same adaptive randomization methodology used in the ongoing Uganda LLIN-UP trial. The process involves: (1) A value of 0 or 1 is randomly assigned to each cluster (zone), with assignment of the first cluster from a coin toss. (2) Cumulative probability ranges are generated for each net type based on the targeted number of each individual type of net / targeted number of total nets. (3) The second cluster is assigned to intervention-arm based on which cumulative probability range the corresponding random number fell into. (4) Steps 2 and 3 are repeated after removing the number of targeted nets assigned to the cluster for the corresponding type of net and the total number of nets. (5) The process is repeated until all clusters are allocated to an intervention.

The geography of the LLIN distribution plan is shown in Figure 6. Although during our scoping visit we were unable to obtain accurate information on travel times from Gemena to outer locations, our experience during recent visits suggests that travel times are unlikely to exceed an average rate of 30km/ hour and may be slower after heavy rains.

IMA world health will be organizing the logistics of the LLIN distribution including a per house hang-up programme involving GPS location of every house.

Boto mixed LLIN distribution zone

Figure 6. Map of Sud Ubangi health zones showing those randomised to receive PBO LLINs (blue); standard LLINs (white) or a mixed zone (blue/white)

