There needs to be one mixed assignment zone (Boto), which will primarily be a non-PBO distribution (see Table). For reasons of study power (below) it is crucial to organise the distribution such that the net types cluster around health centres used for assessment, to ensure that the zone can be retained as a cluster for at least one and hopefully both LLIN types in the study. The number of available PBO LLINs represents just under 25% of the total net need for Boto. As a result of logistical considerations and also to reduce the potential for mosquito dispersal between clusters with different types of LLIN a distribution plan to a cluster of western aires de sante is proposed for Boto (Figure 7).

Figure 7. Map of Boto health zone showing the western areas of Bomele, Bombili, Bobandu and Bokozo proposed to receive PBO LLINs (blue); all other areas will received standard LLINs. ?-1,2 show uncertain boundary locations between zones

If projected LLIN needs for each of the four areas are accurate, this would leave 2,000 surplus PBO LLINs, which could be distributed as close as possible, i.e. preferably along borders of these aires de sante to expand the size of the PBO-LLIN cluster.

More generally the mixed distribution in Boto could provide an important template for future distributions to provinces where division into fewer zones would preclude a statistically-useful comparative study if LLINs of contrasting types were distributed solely at the zonal level. Whilst statistically a distribution fully randomized at the level of aires de sante would be powerful, this is logistically challenging, may lack visible mapped impact on a malaria data map. Grouping of aires de sante - in the way proposed for Boto - could provide a viable intermediate distribution plan to meet statistical requirements, and, in addition to relative logistical ease also has the advantage of reducing the impact of human, net and mosquito movements among net-type clusters.

Proposal hypotheses and endpoints

Epidemiological

Primary

Hypothesis: PBO LLIN distribution will result in a lower malaria prevalence than standard (non-PBO) LLINs as indicated by reduced prevalence in ANC1 visitors.

Endpoint: monthly malaria prevalence in ANC1 visitors measured using RDTs, with main assessment points at 6 monthly intervals and intermediate assessments quarterly.

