Sample size calculation and power: From preliminary analyses it was evident that a minimum 8 vs 8 cluster/ arm trial would be required to adequately power the study to detect plausible effect sizes using a relatively simple cluster arm comparison for a single month's data (temporal variation is unknown so it is difficult to include multiple months in *a priori* power analysis). We used fixed assumptions for the number of available health centres/ zone of N=7 and number of ANC1 visitors

per month of N=20, giving a cluster size of N=140. Note that varying the cluster size has only a moderate impact on power, provided health centres are chosen randomly from those available. Parameter values for the inter-cluster coefficient of variation (*k*, which has a large impact on power) were estimated from DHIS2 2018 data from the rate of positive malaria tests per month per capita (i.e. data divided by population size of zone) as a proxy. Following equation 9 in Hayes & Bennett (1999) we calculated k=0.18 from these data. However, noting this is lower than estimated from the only comparable published study from Tanzania (k values of 0.20-0.28 depending on survey round; West et al. 2014) we also examined a 'high COV' value of k=0.3.

Similarly we lacked information on the baseline prevalence of malaria for Sud Ubangi, with the last survey in 2013-14 detecting a rate of 24% in children under 5 (MPSMRM 2013-14), which using a conversion factor of 1.44 between child and pregnant women's prevalences (van Eijk et al. 2015) we used to estimate an ANC prevalence value of 17%, which is also very close to the average figure for the DRC ANCs presented in Hellewell et al. (2018). However, figures in Hellewell vary greatly and thus because of the considerable uncertainty in this point estimate, we examined a range of possible prevalence rates (applicable to the standard-LLIN reference arm).

We identified the minimum detectable reduction in prevalence using equation 4 from Hayes & Bennett (1999) with the following study design parameters:

Arms=2; Clusters (zones)/arm = 8; subjects/ cluster = 140; k = 0.11 or 0.30; α =0.05; power =80%; prevalence in reference standard-LLIN arm (π 0) varied between 5 and 50%

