Results are shown in Figure 8, and suggest that the study design proposed will be capable of detecting a reduction in prevalence of less than the maximum obtained in the Tanzania Olyset + PBO LLIN trial (Protopopoff et al. 2018) even with the higher COV unless prevalence rates are much lower than expected and if the lower COV value is realistic the study has good prospect to detect the lower effect size seen in the Tanzania study with likely prevalence rates. Our data from Nord Ubangi suggest a greater entomological efficacy of Permanet 3 than Olyset + (Figure 3) but it is unclear whether this might translate into a larger epidemiological effect size than

Figure 8. Summary of power for ANC1 prevalence study based on sample size projections of 8 health zones/ arm, 7 health centres/ zone, 20 ANC1 visitors tested per month for two different values of the intercluster coefficient of variation. The plot shows the minimum % reduction in monthly prevalence in PBO vs non-PBO LLIN arms predicted to be detectable (with 80% power) as a function of *Plasmodium* prevalence in ANC1 visitors. Maximum and minimum % reduction estimates obtained in the Tanzania PBO (olyset +) vs standard (olyset) LLIN trial (Protopopoff et al. 2018) are superimposed for context.

obtained in the Tanzania Olyset+ trial. The split zone in Boto could provide one additional non-PBO cluster, if the distribution occurs as planned and can include sufficient health centres, but at present the sample size calculations and power analysis conservatively retain the 8 vs 8 design.

Procedures

ANC visitor recruitment

The recruitment process at each clinic will occur when women attend their first (second trimester) ANC appointment. Women will be asked if they would like to be enrolled in the study, the main

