implication of which for them is shown in the flow diagram below, i.e. they will be tested for malaria whether symptomatic or not. It will be made clear that there is no accepted benefit of either, and that the option is being offered solely for the purposes of our LLIN evaluation study. If, after asking any questions and discussing with friends or relatives as desired, they agree and sign the consent form, they will proceed via the lower route shown in the figure. If they do not wish to be included they will follow the route shown in the upper part of the diagram, which represents standard care. The decision will need to be taken within the timeframe of the appointment, and if a clear and certain decision is not reached by this time the standard care route will be followed.

Inclusion of health centres (aires de sante) in the study

The aires de sante (N=7) from each zone de sante (N=16) to be included in the study will be identified by random allocation from a list of functional aires de sante in a zone with >20 ANC1 visitors per month based on 2018 DHIS2 data.

Data collection and collation

Data collection should start at the first possible ANC before or just after (determined by RDT/ACT supply and training logistics) LLIN distribution. Recordings preceding the distribution would be beneficial but are unlikely to be feasible owing to time constraints.

It is proposed that study RDT results are recorded separately on the questionnaire form (appended) and transferred to the ANC register (observations section), rather than as a suspected or tested case in the standard register, which is the current procedure. The simple questionnaire will collect only essential information about the participant and their home environment as pertains to malaria risk and should be readily completed within the time waiting for the RDT result. Variables generated from the questionnaire data may serve as covariates in analyses although this is not planned *a priori*. ACT treatment would be administered to women testing positive in the RDTs. Data collected will be transferred monthly to Gemena in the same way as the DHIS2 data collation process, and passed to the study epidemiological coordinator.

Training

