All data will be analysed primarily on the basis of intention-to-treat. The primary outcome will be the prevalence of parasitaemia from the ANC visitor surveys, which will be compared between treatment arms using generalized linear Poisson mixed models with log link function to allow assessment of intra-cluster correlation, and correction factor to maintain type I error rate with a small number of clusters, but maintain power for the number of clusters in our study (Leyrat et al. 2017). Continuous (monthly) data will be available for each major endpoint analysis and will be analysed with time since LLIN distribution as a covariate. However, the power analysis above is based on separate monthly assessments. Interim endpoint analyses will be conducted quarterly, to allow ongoing assessment of the trial by funders. Meaningful baseline data will not be available for the study and therefore it is not intended to perform adjusted analyses *a priori*, though if systematic differences in influencing factors are identified, covariates may be incorporated into analyses. Blinding at the level of data collection is not possible because of the ready identifiability of the different types of LLINs. However, data source will be encoded prior to statistical endpoint analysis to ensure blinding.

Entomological

Primary

Hypothesis: PBO LLIN distribution will reduce the benefit of P450 metabolic-based enzymes and arrest selection on a key genomic area for resistance leading to lower frequencies in PBO-LLIN zones (via stasis or a fall) than observed in zones with standard LLINs (in which an increase is expected). In lay terms this is testing a hypothesis that PBO LLINs will reverse the increase in pyrethroid resistance; an effect which we should be able to capture using informative DNA markers for molecular surveillance.

Endpoint: comparative annual resistance marker frequency in *An. gambiae* measured using molecular surveillance diagnostics

Sample size calculation and power:

Entomological indices can be readily assessed at intervals with a periodicity of 6 months suggested as providing a good timeframe for a hypothesised change in marker frequencies. The work is

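### The stated design of 8 zones per arm with 7 centres each does not match the allocation table, which gives 9 non-PBO (counting Boto) and 7 PBO zones; the eighth PBO cluster is a non-randomised part of Boto

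*Protocol*

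**What the plan says.** The epidemiological sample size section calls 8 vs 8 the minimum needed and sets its parameters as "Clusters (zones)/arm = 8; subjects/ cluster = 140; k = 0.11 or 0.30", with "α =0.05; power =80"%. It adds that Boto might yield one extra non-PBO cluster but that the calculations "conservatively retain the 8 vs 8 design". The epidemiology design summary repeats 8 zones per arm and 7 centres per zone.

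The allocation table, under the randomisation and distribution plan, gives Boto's final assignment as "87,025 Non-PBO + 26,967 PBO". The text beneath explains: "There needs to be one mixed assignment zone (Boto), which will primarily be a non-PBO distribution". The Figure 7 caption names the PBO part: "Bomele, Bombili, Bobandu and Bokozo proposed to receive PBO LLINs".

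The section on inclusion of health centres applies one rule to every zone: "The aires de sante (N=7) from each zone de sante (N=16) to be included in the study will be identified by random allocation". It makes no exception for Boto. The epidemiological data analysis section opens: "All data will be analysed primarily on the basis of intention-to-treat".

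**The concern.** Cluster count, arm membership and centre selection are all fixed in this protocol, and for Boto they do not agree. The randomisation section describes a zone drawn to non-PBO and split because the non-PBO stock ran short. The power section and design summary need an eighth PBO zone with 7 randomly chosen centres, and no such zone exists in the table. The centre-selection rule would draw 7 aires from the whole of Boto, although the distribution plan wants net types grouped around the assessed centres.

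At stake is whether every cluster in the primary comparison reached its arm by randomisation. With only 15 or 16 clusters and, as the protocol says, no meaningful baseline data, any imbalance brought in by a hand-chosen part-zone could not be checked.

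**Working it through.** **1. Replaying the allocation table.** The first row implies a starting stock of 933,500 nets of each type (847,237 + 86,263 = 933,500; PBO remainder 933,500). Subtracting each zone's need in order reproduces every remainder.

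| Group | Zones | Net need |
|---|---|---|
| Whole non-PBO | 8 (Budjala, Bogosinubia, Libenge, Mawuya, Bulu, Kungu, Bominenge, Ndage) | 933,500 − 87,025 = 846,475 |
| Whole PBO | 7 (Bwamanda, Gemena, Mbaya, Tandala, Bangabola, Bokonzi, Zongo) | 933,500 − 26,989 = 906,511 |
| Split | 1 (Boto) | 113,992 |

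At Boto's row the non-PBO remainder goes from 87,025 to 87,025 − 113,992 = −26,967, and the PBO remainder stays at 76,596. The draw was therefore non-PBO, and the 26,967 shortfall was met from PBO stock. The protocol does not say this in words; it follows from the remainder column and fits the description of Boto as mainly non-PBO. The draw is 9 vs 7.

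**2. What the eighth PBO cluster can be.** With 7 whole PBO zones, only Boto's PBO part is left. The power section confirms this by treating Boto's non-PBO part as the additional cluster. That PBO part is four aires. The background section gives each aire one health centre or smaller post, so there are at most 4 centres. At the planning figure of 20 women, 4 × 20 = 80 a month, against 7 × 20 = 140. Eligibility requires more than 20 first visits a month, so fewer than four may qualify.

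**3. The centre draw.** PBO nets are 26,967 / 113,992 = 23.7% of Boto's need. With net share as a proxy for centres, an unstratified draw of 7 would include about 7 × 0.237 = 1.7 PBO centres.

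**4. Power.** The plan's formula (Hayes & Bennett, equation 4) is c = 1 + (z₀.₉₇₅ + z₀.₈₀)² [v₀ + v₁] / (p₀ − p₁)², with vᵢ = pᵢ(1 − pᵢ)/n + k²pᵢ². Inputs are p₀ = 17%, n = 140 and c = 8; a two-sided test is assumed because sidedness is not stated. The text derives k = 0.18 but the parameter line says 0.11, so 0.11, 0.18 and 0.30 are all shown. For unequal arms, each vᵢ is divided by that arm's clusters minus 1.

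Minimum detectable reduction at 80% power:

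| Design | k = 0.11 | k = 0.18 | k = 0.30 |
|---|---|---|---|
| 8 vs 8 | 29.8% | 34.4% | 44.2% |
| 9 non-PBO vs 7 PBO | 29.7% | 34.1% | 43.4% |
| 8 vs 7 (Boto excluded) | 30.6% | 35.3% | 45.0% |
| 8 vs 7 plus a Boto cluster of 80 | 30.2% | 34.8% | 44.4% |

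Figure 8 is not available, so the plotted values could not be compared.

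Power at the 8 vs 8 detectable effect comes from a noncentral t on cluster proportions, with df = clusters − 2. For k = 0.18: p₁ = 0.1115, difference 0.0585, v₀ = 0.001944, v₁ = 0.001110.

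- 8 vs 8: SE = √(v₀/8 + v₁/8) = 0.01954; ratio 2.995; df 14; power 79.5%.
- 9 vs 7: SE = √(v₀/9 + v₁/7) = 0.01936; ratio 3.024; df 14; power 80.3%.
- 8 vs 7: SE = √(v₀/8 + v₁/7) = 0.02004; ratio 2.920; df 13; power 77.0%.

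Over the three k values, 9 vs 7 gives 79.8–81.1%, 8 vs 7 gives 76.8–77.5%, and 8 vs 7 plus the small Boto cluster gives 78.3–79.1%.

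**5. Strict intention-to-treat.** If all sampled Boto centres stay non-PBO, the contrast shrinks by about 0.237/9 = 2.6% on the net-share proxy. Power in the 9 vs 7 layout is then about 78–79%.

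**The case against.** The split is disclosed openly. The distribution plan hopes to keep Boto as a cluster for one or both net types, the power section treats its non-PBO part separately, and the entomological sample size section samples PBO and standard clusters within Boto. The protocol clearly thinks of Boto as two clusters by net type. The final-assignment column records the split before distribution, so analysing each part by its assigned net does not plainly breach intention-to-treat. Twenty women per centre is a planning minimum, so 80 is not a cap. Calling the count conservative is also fair for the non-PBO arm: 9 vs 8 would give 82.5–83.1% power, and the plan declines to claim it.

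All of this stands, but it does not rescue the PBO arm. The same caution is not applied there, where the doubtful part-cluster is counted. More women per centre does not turn four centres into seven or make the choice of aires random.

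A reader might infer that the arm effect will be diluted: if Boto were sampled zone-wide and then coded PBO, the dilution would be (1 − 0.237)/8 = 9.5% and power about 71%. The documents do not support this as the expected outcome. No section plans that coding, and the sections just named point the other way. The unstratified draw is a drafting gap.

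A reader might also infer that the primary contrast must be biased. Using the western aires carries a risk of bias in one cluster, of unknown direction and size; nothing in the protocol shows that it is present.

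**Conclusion.** The statement of 8 zones per arm with 7 randomly chosen centres each is wrong as written. The table gives 8 whole non-PBO zones, 7 whole PBO zones, and Boto, in effect drawn to non-PBO. The eighth PBO cluster rests on four aires that were not randomised and offer at most 4 of the 7 centres. The word conservative holds for the non-PBO arm only.

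The power consequence is slight: from a marginal gain (9 vs 7) to a loss of 2 to 3 points (8 vs 7) relative to 79.5%. This rests on 17% reference prevalence, a two-sided 5% test and k between 0.11 and 0.30; the choice between k = 0.11 and 0.18 moves the detectable reduction more than the cluster count does. The weight of the point lies in the randomised comparison and in the conflict between the randomisation section and the power, centre-selection and design-summary sections. It should be fixed, but it does not undermine the trial.

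**What to change.** - Restate the design as 9 non-PBO vs 7 PBO zones in the power section and design summary, and redo the power figure on those counts.
- Amend the centre-selection rule so that Boto's centres are drawn by net type.
- In the primary analysis, keep Boto in its drawn non-PBO arm, using centres from its non-PBO aires. Confirm that 7 eligible centres remain once the four western aires are removed; otherwise state the smaller number. The protocol assures only at least 7 suitable centres per zone.
- Restricting Boto to its non-PBO aires is not strictly as drawn, because it uses the complement of the same non-random choice. Add a sensitivity analysis keeping all sampled Boto centres as non-PBO, and another excluding Boto (8 vs 7).
- Use the Boto PBO aires as a separate cluster in a sensitivity analysis only.
- Apply the same rule to the DHIS2 case outcomes, whose denominators are population estimates per health zone.

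The cost is protocol wording and one stratified draw, with essentially no loss of power if 7 eligible non-PBO centres remain in Boto. It is best done before centres are drawn, since selection is hard to repair once testing has begun.

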powered however for a 12-month comparison which it is anticipated would come from comparisons of collections made initially at 0 vs 12 months, but with additional comparisons (subject to study continuation) at 6 vs 18 months etc. We base calculations on a current base resistance marker frequency (the Cyp6 gene-cluster marker haplotype described above) of 0.72, which is based on recent local data we have obtained. A projected 5% annual decrease in the PBO arm and 5% increase in the standard LLIN arm, translates into a projected difference between arms of approximately 10% per year. The total number of *An. gambiae* required per collection period to detect such a difference as significant (using an exact test) is N=1392 (allowing a two-fold higher collections in standard-LLIN houses than PBO-LLIN houses). Clustering is not accounted for in the analysis because we postulate (based on general patterns for the species) that it is unlikely there will be significant *a priori* population genetic structure within the *An. gambiae* population of Sud Ubangi.

Allowing for 16% non-*An. gambiae* in collections (based on our data from neighbouring Nord Ubangi province; Lynd et al. 2018) equates to a total of 1,650 Anopheles per survey period. Allowing for an average catch of N=3 *An. gambiae* per standard-LLIN house, and 1.5 in PBO LLIN houses this would require a total number of N=734 houses to be sampled by prokopack collections during each collection around the 6 month periods. We will sample from 4 clusters per arm to reduce travel costs and time). Specifically, we will sample from 3 separate health zones per arm and then from both PBO- and standard-LLIN clusters within the mixed Boto health zone. Villages to be sampled will be those in close proximity to the health centres included in the epidemiological component of the study.

It is intended that the same houses would be sampled each time, though if this is not possible, or if verbal consent to access to sample is not provided a neighbouring replacement house would be recruited. The projected 10% decrease is annual and therefore the main comparisons would compare surveys separated by 12 months, i.e. months 0 vs 12, 6 vs 18, 12 vs 24, etc.

Secondary entomological outcomes

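### One random draw of seven aires per zone ignores net type in split Boto, so the eighth PBO cluster is left to chance

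*Protocol*

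**What the plan says.** Under the heading on inclusion of health centres, the protocol fixes one rule for the whole province: "The aires de sante (N=7) from each zone de sante (N=16) to be included in the study will be identified by random allocation", the draw being made "from a list of functional aires de sante in a zone with >20 ANC1 visitors per month based on 2018 DHIS2 data". Net type plays no part in it.

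The section on randomisation and the distribution plan makes Boto a split zone. The allocation table gives it "87,025 Non-PBO + 26,967 PBO", and the Figure 7 caption places the PBO nets: "western areas of Bomele, Bombili, Bobandu and Bokozo proposed to receive PBO LLINs (blue); all other areas will received standard LLINs". The same section says that, for study power, "it is crucial to organise the distribution such that the net types cluster around health centres used for assessment". The purpose is to keep Boto usable as a cluster for one net type and, if possible, for both.

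The epidemiological sample size section takes 8 clusters per arm as the minimum, each with 7 centres and 20 first-visit women a month. It mentions Boto's standard part as a possible extra non-PBO cluster. The entomological sample size section uses three zones per arm plus both parts of Boto, and adds: "Villages to be sampled will be those in close proximity to the health centres included in the epidemiological component of the study".

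**The concern.** The selection rule and the plan for Boto do not fit together. The four PBO aires were chosen for logistics and to limit mosquito dispersal, and the draw of centres takes no account of them. In Boto the seven places are therefore shared between net types by chance.

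This matters because Boto's PBO part is not a spare. The table gives eight whole zones to standard nets and only seven to PBO nets, so the eighth PBO cluster for the ANC comparison can come only from Boto. The mosquito villages are tied to the study health centres, so the same draw also decides where Boto's PBO entomology cluster can be sampled.

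**Working it through.** **Inputs from the protocol**
- 7 centres per zone and 20 women per centre per month: 7 × 20 = 140, the cluster size in the power calculation. This reproduces.
- Whole PBO zones in the table: Bwamanda, Gemena, Mbaya, Tandala, Bangabola, Bokonzi, Zongo = 7. Whole standard zones: Budjala, Bogosinubia, Libenge, Mawuya, Bulu, Kungu, Bominenge, Ndage = 8. Boto is mixed.
- PBO share of Boto: 26,967 / 113,992 = 23.7%, which agrees with the statement "The number of available PBO LLINs represents just under 25% of the total net need for Boto".
- PBO aires in Boto: 4.

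**Assumptions**
- M, the number of Boto aires that pass the ANC1 filter, is not in the text. The section on ante-natal clinic data says every zone has at least 7 centres with at least 20 first visits a month, so the range starts at 7.
- A rough guide to the other end: the four PBO aires need about 26,967 − 2,000 = 24,967 nets, or 6,242 each, and 113,992 / 6,242 ≈ 18. That estimates all aires in Boto, not those passing the filter.
- All four PBO aires are taken as eligible.

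**Number of PBO aires drawn.** With 7 drawn from M, P(x) = C(4,x) · C(M−4, 7−x) / C(M,7), with mean 28/M. For example, at M=16, P(0) = C(12,7)/C(16,7) = 792/11,440 = 6.9%.

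| M | Mean PBO aires | P(all four) | P(none) |
|---|---|---|---|
| 7 | 4.0 | 100% | 0 |
| 8 | 3.5 | 50% (otherwise three) | 0 |
| 9 | 3.1 | 28% | 0 |
| 10 | 2.8 | 17% | 0 |
| 12 | 2.3 | 7% | 1% |
| 16 | 1.75 | 2% | 7% |
| 18 | 1.6 | 1% | 11% |
| 20 | 1.4 | 0.7% | 15% |

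If only three PBO aires pass the filter, the chance of none rises to 15% at M=16 and 25% at M=20.

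**Effect on ANC power.** The unmatched Hayes–Bennett formula is

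c − 1 = (z₀.₉₇₅ + z₀.₈₀)² · [p0(1−p0)/n + p1(1−p1)/n + k²(p0² + p1²)] / (p0 − p1)².

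Take p0 = 0.17, k = 0.18, n = 140 and a 34.4% reduction, so p1 = 0.1115. The bracket is 0.00101 + 0.00071 + 0.00134 = 0.00306, and 7.85 × 0.00306 / 0.0585² ≈ 7.0, which matches c = 8. For unequal cluster sizes, the variance in each arm is the sum of the cluster variances divided by c(c−1). At 17% prevalence the detectable reductions are:

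| k | As planned (8 × 140) | Boto PBO with four aires (80 women) | No Boto PBO cluster (8 vs 7) |
|---|---|---|---|
| 0.11 | 29.8% | 30.2% | 30.6% |
| 0.18 | 34.4% | 34.8% | 35.3% |
| 0.30 | 44.2% | 44.4% | 45.0% |

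The text derives k = 0.18, and the list of design parameters gives 0.11 and 0.30, so all three are shown. The curve in Figure 8 cannot be read here, so these values are not compared with it.

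**The case against.** The strongest reply is that the size of the problem hangs on an unseen number. If Boto has only 7 eligible aires, all are taken and nothing is lost. At M=8 three or four PBO aires are certain, and even at M=10 the chance of three or four is 50% + 17% = 67%. This stands: a reader might infer that the draw will usually leave Boto with a token PBO sample or none, but the text supports that only for larger M.

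The second reply is that power hardly moves. This also stands. Between the best draw and none at all, the detectable reduction changes by half a point at k = 0.18. The protocol itself says cluster size has only a moderate effect, 20 women per centre is a stated minimum, and the monthly data accumulate in a mixed model. A reader might infer serious damage to the primary comparison, and the figures do not show it.

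A reader might also infer that entomology would drop to three PBO clusters if no PBO centre were drawn. The protocol does not say so. It commits to sampling both parts of Boto, so such a draw would put that commitment in conflict with the rule placing villages near study centres.

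Finally, the distribution section says the distribution should be arranged around the assessment centres, and the four aires are described as proposed. The intention is therefore on record. What is missing is a selection rule that carries it out: the aires are named on other grounds and the draw disregards them.

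**Conclusion.** The point holds as a mismatch between the selection rule and the stated need for Boto. Seven whole zones are PBO, eight PBO clusters are required, and the rule leaves the eighth ANC cluster and one of the four PBO entomology clusters to chance. The risk runs from nil at M=7 to a 15% chance of no PBO aire at M=20, assuming all four are eligible. The loss of ANC power is small, so the case rests on securing a cluster the design counts on. The correction should be made before the list is drawn, but the trial does not stand or fall on it.

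Taking all four PBO aires would not restore the planned cluster size. At the minimum of 20 women per centre, the cluster has 4 × 20 = 80 women a month, against 140.

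**What to change.** Add a Boto exception to the rule on inclusion of health centres: draw the centres separately by net type, include every eligible aire among the four PBO areas, and draw the standard aires at random from the remaining eligible ones. Choose the Boto entomology villages from the same stratified list. The standard aires are still drawn at random, and taking all eligible PBO aires is a full count of that part of the zone.

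The change costs one sentence and, if Boto stays at seven centres, no extra sites. It is not free for the standard part. With four PBO aires taken, 7 − 4 = 3 standard centres remain. A reader might think this harmless because eight whole zones already have standard nets, but Boto's standard part is also one of only four standard entomology clusters, the entomology logistics paragraph plans four collection locations in each zone involved, and the protocol hopes to use this part as an additional non-PBO ANC cluster. The sponsor should set the split with both uses in view. Keeping seven standard centres as well would mean up to 7 + 4 = 11 centres in Boto.

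The change is unnecessary if exactly seven aires prove eligible or if Boto is no longer split.
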